	
 1. Those who are allergic to local anesthetics; 2. Those who are unable to cooperate with sports or non-motor function monitoring; 3. Exclude patients with Parkinson's superimposed syndromes, such as corticobasal degeneration, dementia with Lewy bodies, multiple system atrophy, progressive supranuclear palsy; and secondary Parkinson's syndromes, such as vascular parkinsonism, drug poisons or patients with Parkinson's syndrome caused by trauma; 4. Refuse to sign the consent form.

Key Interventions
	
Experimental group: standard treatment of Parkinson's disease + SGB
 
Control group: standard treatment for Parkinson's disease

Follow-up
	
Intervention follow-up period: On Day0, Day5 and Day10 of the first, second and third cycles, the visiting schedule was used to record the required information. The interval of each cycle was 1 month, and the total follow-up time was 3 months.
 
Follow-up period: Modified MDS-UPDRS (Revised Movement Disorders Association Unified Parkinson's Disease Rating Scale) III scores were collected every month after treatment.

Evaluation index
	
Primary end point: MDS-UPDRS score.
 
Secondary end points: NMSS (Parkinson's disease Non-motor Symptom Evaluation Scale), PDQ-39 (39-item Parkinson's disease questionnaire), 10M-WT (walking speed test), H&Y grading (Hoehn Yahr (modified) Parkinson's disease grading), LDE (dopa equivalent dose).

Statistical method
	
SPSS25.0 software was used to analyze the data, and the measurement data were expressed by mean and standard deviation ($\bar{X} \pm S$). For those with normal distribution and homogeneity of variance, paired sample T test was used for intra-group comparison, two independent samples T test was used for inter-group comparison, and t 'test was used for those with uneven variance. The count data were expressed as percentage (%), and the chi-square test was used to compare the total effective rate between groups. $P < 0.05$ was considered as statistically significant difference.

Study time
	
Expected enrollment time of the first subject: 2022-01-01
 
Expected enrollment time of the last subject: 2022-06-30
 
Expected end time: 2024-06-30

Visit Schedule

	Screening stage	Intervention follow-up period			Observational follow-up period	Exit supervision
		Into the group	Follow-up 1	Follow-up 2	Follow-up 3	

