4.2 Grouping method and blinding level

Grouping: The study was divided into an experimental group (standard antiparkinsonian therapy + SGB) and a control group (standard antiparkinsonian therapy).

Random: Use a stratified randomization method. Group study subjects by age. After grouping, there will be 2 subgroups: ① patients aged 45-60 years, ② patients aged 61-80 years. The 2 subgroups were divided into the experimental group and the control group according to 1:1, and finally the experimental group and the control group in the 2 subgroups were pooled.

Open: Both investigators and patients were aware of the grouping of patients.

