7.2 Dosage and start and end times

Test group: Oral standard anti-Parkinsonian drugs, including compound levodopa, pramipexole hydrochloride, ropinirole, entacapone, amantadine, antan, etc. A total of three cycles of stellate ganglion block were performed, with 10 stellate ganglion blocks per cycle (once a day), with a 20-day interval between the two cycles;

Control group: Oral standard antiparkinsonian drug

8. Research Process

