9.2 Criteria for discontinuation of study treatment

Criteria for subjects to discontinue study treatment are as follows:

(1) Subjects withdrew their informed consent for any reason or no reason and refused to continue receiving study drug treatment;

(2) According to the judgment of the investigator, the subject's clinical symptoms have deteriorated/physical condition has decreased, the study endpoint has been reached, or there are intolerable side effects, including any abnormal clinical or laboratory tests or other medical conditions;

(3) Other circumstances that the investigator deems necessary to terminate the study drug treatment;

(4) The sponsor terminated the study.

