9.3 Steps to withdraw from the study or discontinue study treatment

Subjects must be checked for efficacy and safety in accordance with the protocol for withdrawal from the study and final observation and follow-up, and AEs and outcomes must be fully recorded. The researcher can suggest or provide alternative treatment methods to the subjects according to the actual situation of the subjects.

If the subject refuses to come to the research center for further visits, their survival status should continue to be tracked unless the subject withdraws informed consent. In this case, no further study evaluations should be conducted and no further data should be collected.

10. Evaluation indicators

10.1 Primary endpoint: Modified MDS-UPDRS scale score (the revised version of the Movement Disorders Association Unified Parkinson's Disease Rating Scale, which has four main parts, including both physician and patient aspects, the first part is psychological, behavioral and emotional; the second Part is activities of daily living; the third part is motor symptoms; the fourth part is complications), SGB is carried out in three cycles, each cycle is carried out for 6-10 days, and the interval between each cycle is 20 ± 7 days; The first, second, and third cycles of Day0, Day5, and the last day were measured and recorded.

10.2 Secondary endpoints : NMSS (Non-motor Symptom Evaluation Scale), PDQ-39 (Self-rating scale for clinical evaluation of the quality of life in patients with Kinson's disease), H&Y classification (Classification of Parkinson's disease), LDE (levodopa equivalent dose), 10M-WT (10m walk test), cerebrospinal fluid and blood biomarkers, SGB were carried out for a total of three cycles, each cycle was carried out for 6-10 days, and the interval between each cycle was 20 ± 7 days; On Day0, Day5, and the last day of the third cycle, the scale data were measured and recorded. The researchers performed head MRI + susceptibility-weighted imaging on Day 0 of the first cycle and Day 10 of the third cycle, respectively, to compare the changes in the "swallowtail sign" of two successive head MRIs.

11. Adverse events, serious adverse events, adverse reactions

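### Section 10.1 reads the primary score on the last day of a 6-10 day block cycle of unruled length and gives controls no matching day, so the reading day could follow response in one arm only

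*Protocol*

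**What the plan says.** Section 10.1 of the protocol describes the course as "SGB is carried out in three cycles, each cycle is carried out for 6-10 days, and the interval between each cycle is 20 ± 7 days", and sets the readings of the primary score in the same sentence: "The first, second, and third cycles of Day0, Day5, and the last day were measured and recorded". Section 10.2 uses the same scheme for the secondary scales in the third cycle. Neither section says who fixes the length of a cycle, when, or on what grounds.

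Three other parts bear on this:

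- **Masking (4.2):** "Both investigators and patients were aware of the grouping of patients". No masked assessor is described.
- **Control arm (7.2):** "Control group: Oral standard antiparkinsonian drug". There is no block course, so the control arm has no day on which one ends.
- **Stopping study treatment (9.2, item 2):** one ground is that "the study endpoint has been reached". The primary endpoint is a scale score, and no state that would count as reaching it is defined.

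Elsewhere the timing is fixed. The synopsis records data "On Day0, Day5 and Day10 of the first, second and third cycles". Section 7.2 describes three cycles "with 10 stellate ganglion blocks per cycle (once a day), with a 20-day interval between the two cycles". The visit schedule and section 8.3 place the MDS-UPDRS at 4, 8 and 12 weeks without distinguishing the arms. Section 10.2 puts the second MRI on Day 10 of the third cycle.

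**The concern.** A randomised comparison needs the outcome read at a time that does not depend on the outcome, and at the same time in both arms. Section 10.1 secures neither for its last reading in each cycle. That reading is tied to the end of the block course, and the course may end on any of several days. If it tends to end when a patient looks well and to continue when not, the block arm is read on favourable days. The control arm has no such mechanism, and any day used for it has to be invented. The difference would then lean towards the block even if the block did nothing, and randomisation gives no protection because the selection happens afterwards.

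This is related to the timing conflict between sections but is not the same thing. If the sponsor resolved the conflict by letting 10.1 govern, as the section that defines the endpoint, the contradiction would disappear and this weakness would remain.

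**Working it through.** **1. The plan's own figure.** Section 4.3 gives SD 9.58, difference 10, Z values 1.96 and 0.84, and 20% loss. n = 2 × (1.96 + 0.84)² × 9.58² / 10² = 14.39, rounded up to 15. Then 15 / 0.8 = 18.75, rounded up to 19 per arm and 38 in total. This reproduces. The point does not rest on it, but the 10-point difference is the yardstick below.

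**2. The passages side by side.**

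| Place | Length of cycle | Reading day | Same in both arms? |
|---|---|---|---|
| 10.1 | 6-10 days | Day 0, Day 5, last day | No last day for controls |
| Synopsis, Follow-up | not given | Day 0, 5, 10 | No split by arm |
| 7.2 | 10 daily blocks | not given | Blocks in one arm only |
| Visit schedule, 8.3 | not given | 4, 8, 12 weeks | No split by arm |
| 10.2, MRI | 6-10 days | Day 0 of cycle 1, Day 10 of cycle 3 | No split by arm |

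No text ranks these.

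**3. Size if only the Day 5 score leads the length.** Assumptions:

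- The block has no effect.
- The day-to-day SD within a patient is 3 to 5 points (the protocol gives none).
- Days have first-order autocorrelation ρ.
- The shortest cycle ends on Day 6 and the longest on Day 10.

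The most favourable rule ends on Day 6 if the Day 5 score is better than the patient's own average, and otherwise on Day 10. For a standard normal Day 5 deviation, each half contributes 0.399 times its correlation with the day read, so the false benefit is

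0.399 × (ρ − ρ⁵) SD.

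- ρ = 0: 0
- ρ = 0.5: 0.399 × (0.5 − 0.031) = 0.19
- ρ = 0.8: 0.399 × (0.8 − 0.328) = 0.19
- maximum, where 5ρ⁴ = 1 (ρ ≈ 0.67): 0.399 × 0.535 = 0.21

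In points the ceiling is 0.21 × 3 ≈ 0.6 to 0.213 × 5 ≈ 1.1. A simulation with 15 evaluable patients per arm, total SD 9.58 and 10% or 30% of the variance day to day gave 0 to 1.0 point and a two-sided type I error of about 0.05 to 0.06.

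**4. Size if daily judgement on days 6 to 10 tracks the score.** This needs information that 10.1 does not schedule.

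- *Best sequential rule, independent days:* v₁ = 0 and v(k+1) = φ(v) + vΦ(v) give 0.399, 0.630, 0.790 and 0.913 SD. At SD 5 this is 0.913 × 5 ≈ 4.6 points, the worst case.
- *Cruder rule* (end on the first day at least 0.3 SD better than average, otherwise Day 10; 200,000 simulated patients): 0.85, 0.58 and 0.28 SD at ρ = 0, 0.5 and 0.8. The low end is 0.28 × 3 ≈ 0.8 points.
- *End on the first day better than the patient's own average* (independent days, 5% to 30% of the variance, that is SD 2.1 to 5.2): 1.6 to 3.9 points, with a two-sided type I error of 0.07 to 0.20.

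**5. With one fixed day in both arms.** The simulated bias is about 0 and the type I error about 0.05. The sample size stays at 19 per arm.

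**The case against.** The strongest reply is that the mechanism is inferred. A reader might conclude from 10.1 that investigators choose the cycle length after seeing the Day 5 score. No passage says so; the protocol is silent and merely has no rule against it. This stands, and the point is confined to what the text leaves open.

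A reader might also take 9.2(2) as licence to end a cycle once a patient has done well. It does not support that. It governs stopping study treatment altogether, not closing one cycle before the next, and the neighbouring grounds (deterioration, intolerable side effects) stop patients who are doing badly. What remains is that its endpoint clause is undefined.

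A third tempting inference is a bias approaching half of the planned difference. That figure needs a usable reading on each of days 6 to 10 and independent days. The only scheduled score before the decision is Day 5, and with independent days that score predicts nothing about later ones.

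Three further limits stand. The fixed timings elsewhere would close the gap if they governed. The last day is only one of three readings per cycle, and no single primary time point is named, so the bias enters the primary comparison only if that reading is used. Day numbering is also not settled: if Day 0 is itself a block day, a 6-day cycle ends on Day 5 and the calculation in step 3 would change.

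None of this supplies the missing rule or gives controls a matching day under 10.1.

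**Conclusion.** The point holds in a limited form. Section 10.1 ties the last primary reading of each cycle to the end of a course of unruled length, in an open-label trial, with no counterpart for controls. It conflicts with four other places that fix the timing, and nothing says which prevails. This is an available route to bias in one arm, not a demonstrated bias.

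Its size is not known from the protocol. With an assumed day-to-day SD of 3 to 5 points and the shortest cycle ending on Day 6, it is 0 to about 1.1 points (at most 0.21 SD, or 11% of the planned 10) if the Day 5 score alone leads the length. Up to about 4.6 points is a worst case that rests on informal daily judgement tracking the score. It should be corrected because the remedy is nearly free, not because a large distortion has been shown.

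**What to change.** - In 10.1 and 10.2, replace the last-day reading with one fixed calendar day counted from Day 0 of each cycle, the same in both arms and taken however many blocks were given. The synopsis already uses Day 10, as does the MRI in 10.2.
- Give control patients the same cycle calendar, starting from randomisation.
- Record for each cycle the number of blocks delivered and the reason it ended.
- The sponsor must reconcile the cycle length in 7.2 with that in 10.1, align the synopsis and the 4, 8 and 12 week visits with the chosen reading days, and resolve the undefined endpoint clause in 9.2(2). Which cycle length or stopping rule is right is a clinical matter and is not proposed here.

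The cost is protocol wording, plus one reading a few days later for patients whose blocks end early (at most 10 − 6 = 4 days if Day 10 is kept). The sample size does not change.

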Title	Stellate Ganglion Block in Patients With Advanced Primary Parkinson' s Disease: a Small, Open, Randomized, Controlled Clinical Study
Bidders	Zhujiang Hospital of Southern Medical University
Leader of the unit	Zhujiang Hospital of Southern Medical University
Research purpose	
Main research purpose: To confirm that stellate ganglion block can improve motor symptoms in patients with Parkinson's disease.
 
Secondary research objectives: To determine the efficacy of stellate ganglion block in improving non-motor symptoms, activities of daily living and medication dosage in patients with primary Parkinson's disease.

Research hypothesis	Stellate ganglion block can improve motor and non-motor symptoms in patients with primary Parkinson's disease.
Study design	Single-center, randomized, open-label
Sample size	This study was a randomized controlled trial. The experimental group was treated with standard Parkinson's disease treatment + stellate ganglion block (SGB), and the control group was treated with standard Parkinson's disease treatment. According to the literature review and previous clinical observations, the standard deviation of the MDS-UPDRS scale score in the control group was 9.58 points, and the MDS-UPDRS-III score in the experimental group was expected to decrease by 10 points. 80%, and the loss to follow-up rate was 20%. According to the formula for calculating the sample size, 19 subjects were required to be studied in each of the experimental group and the control group, and at least 38 subjects were included in total.
Research object	
Diagnostic criteria: Parkinson's disease patients who met the 2016 MDS criteria for "probable PD" or "diagnosed PD"
 
Inclusion criteria:
 
 1. Age 45-80 years old; 2. Patients with Parkinson's disease who meet the diagnostic criteria of "probable PD" or "diagnosed PD" in MDS in 2016; 3. The patients or their legal guardians agree to participate in this trial and sign the informed consent form; 4. Hoehn-Yahr (H&Y) level 3 to 5; 
Exclusion criteria:

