4.3 Sample size calculation

This clinical trial adopts the sample size calculation formula of 2 groups of quantitative data.

$$n = \frac{(Z_{\alpha} + Z_{\beta})^2 * 2\sigma^2}{\delta^2}$$

Calculation formula:

n represents the sample size of each group.

Take α as 0.05, Z value as two-sided, $Z_{\alpha} = 1.96$; β as one-sided, take power (test power) as 0.8, $Z_{\beta} = 0.84$.

σ represents the difference between the standard deviations of the treatment group and the control group, which is about 9.58 according to previous observations; δ represents the difference of the mean, that is, the difference between the mean of the treatment group and the control group, which is 10; the loss to follow-up rate is 20%.

According to the formula for calculating the sample size, there were 19 subjects in each of the experimental group and the control group, and a total of 38 subjects were included.

5. Subject recruitment

A total of 38 middle-advanced primary PD patients and controls who met the requirements in the inpatient or outpatient department of neurology of Zhujiang Hospital were continuously recruited.

6. Research subjects

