13.2.6 Effectiveness Analysis

① **Primary endpoint:** Modified MDS-UPDRS scale score

Measurement data were expressed as mean \pm standard deviation ($\bar{x} \pm s$). For those with normal distribution and homogeneous variance, paired-samples t-test was used for intra-group comparison, two independent samples t-test was used for inter-group comparison, and t' was used for unequal variances. test. $P < 0.05$ was considered to be statistically significant.

② **Secondary endpoints:** NMSS scale, PDQ-39 scale, H&Y grade, LDE, 10M-WT, cerebrospinal fluid blood biomarkers, MRI+SWI changes

Measurement data were expressed as mean \pm standard deviation ($x \pm s$). For those with normal distribution and homogeneous variance, paired-samples t-test was used for intra-group comparison, two independent samples t-test was used for inter-group comparison, and t' was used for unequal variances. For skewed data, median + interquartile range ($m \pm Q$) was used, and nonparametric test was used; $P < 0.05$ was considered statistically significant.

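### No masked reading is provided for the MRI swallowtail-sign comparison in an open trial, so expectation could bias this secondary endpoint; scoring stored scans masked to arm and scan order would be a cheap improvement

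*Protocol*

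**What the plan says.** The synopsis gives the design as "Single-center, randomized, open-label". Section 4.2 adds that "Both investigators and patients were aware of the grouping of patients".

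Section 10.2 sets the imaging endpoint: "The researchers performed head MRI + susceptibility-weighted imaging on Day 0 of the first cycle and Day 10 of the third cycle", with the purpose "to compare the changes in the 'swallowtail sign' of two successive head MRIs". Section 13.2.6 lists "MRI+SWI changes" among the secondary endpoints and plans both within-group and between-group tests for that list.

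The protocol does not say who reads the scans, how the sign is graded, whether the two scans are viewed together, or what the reader knows. It mentions no masked, independent or second reader, and nothing about hiding scan dates or order.

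**The concern.** The swallowtail sign is judged by eye, and the endpoint is a judgement of change. If the reader knows the arm, hope for the block can tilt the between-arm comparison. If the reader knows which scan is later, the same hope can tilt the within-arm paired comparison, even with the arm hidden. Masking the arm alone would leave this second route open.

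Most other secondary measures (NMSS, PDQ-39, H&Y grade, walking test, levodopa equivalent dose) are live ratings, self-reports, performance tests or dosing decisions, which cannot be re-masked afterwards. Stored images can be, without touching the open design. If the protection is not written in, an apparent imaging improvement would be hard to tell from a reading artefact.

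**Working it through.** **1. The plan's own figure.** The imaging endpoint has no stated sample size or error rate. The only figure to reproduce is the primary-endpoint sample size in section 4.3 (α = 0.05 two-sided, power 0.8, σ = 9.58, δ = 10, 20% loss):

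n = 2 × (1.96 + 0.84)² × 9.58² / 10² = 14.39, rounded up to 15 per arm. Then 15 / (1 − 0.20) = 18.75, rounded up to 19 per arm, 38 in total.

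This agrees with the protocol. Below, 19 per arm means all patients scanned twice, and 15 means those left after the planned loss.

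**2. What is written and what is inferred.**

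| Element | Status |
|---|---|
| Investigators know the arm | Written, 4.2 |
| Researchers obtain two scans to compare change in the sign | Written, 10.2 |
| Imaging change is tested within and between groups | Written, 13.2.6 |
| The reader is one of those investigators | Inferred; no reader is named |
| The reader knows which scan is later | Inferred from the reference to two successive scans |
| Reading masked to arm or order | Not provided for anywhere |

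**3. Illustration of the between-arm bias.** Every rate here is an assumption. There is no true change. A share p0 = 5% of control pairs is read as improved through noise, and expectation raises the share to p1 in the block arm only. The chance of a false significant difference is the sum, over all pairs of counts (a in control, b in block) for which Fisher's two-sided test gives P < 0.05, of Bin(a; n, p0) × Bin(b; n, p1).

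Example at n = 19, p1 = 25%. With 0, 1, 2 or 3 improved readings in control, significance in favour of the block needs at least 5, 7, 9 or 10 in the block arm:

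0.3774 × 0.5346 + 0.3774 × 0.1749 + 0.1787 × 0.0287 + 0.0533 × 0.0089 = 0.2018 + 0.0660 + 0.0051 + 0.0005 = 0.273. The remaining terms are negligible.

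| Block-arm rate | 19 per arm | 15 per arm |
|---|---|---|
| 5% (read alike) | 0.2% | 0.1% |
| 10% | 1.4% | 0.6% |
| 15% | 6.1% | 3.0% |
| 25% | 27.3% | 16.7% |
| 35% | 55.5% | 39.6% |

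**4. Sensitivity to the test.** The protocol does not name Fisher's test. It names t-tests or nonparametric tests for this endpoint and a chi-square test for the total effective rate. With an uncorrected chi-square test and control rates from 5% to 20%, an added 10, 20 or 30 percentage points in the block arm gives 11–14%, 28–42% or 53–69% at 19 per arm, and 9–10%, 23–31% or 42–58% at 15 per arm. With equal rates the chance is 0.5–5.0%. The pattern is the same and the levels are higher.

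**5. Within-arm bias.** The documents offer no basis for a figure, and none is given.

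**The case against.** A reader might infer that the protocol describes an unmasked reading, with a labelled before/after pair shown to someone who knows the arm. It does not. Section 10.2 names no reader, display or labelling; section 4.2 speaks of investigators, and a radiologist outside the team could do the reading. Section 14.1 also leaves judgement standards to operating procedures agreed before the start. This stands as far as it goes: the defect is a missing provision, not a stated bad practice. But section 14.1 does not promise masking, and what an outcome assessor may know belongs with the blinding and endpoint sections of the protocol.

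A reader might also infer that a false imaging result is likely. The documents do not support that. All rates are assumed. If expectation doubles or triples a 5% noise rate, the Fisher figures stay between 0.6% and 6.1%, near or below the nominal level. Only a five- to sevenfold rise gives 17–56%.

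Nor can it be assumed that stripping labels masks the reader completely. Section 8.1 allows routine-care imaging to serve at screening, so a reader may already have seen a scan clinically.

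Finally, the endpoint is secondary, and open rating of the primary MDS-UPDRS is the weightier form of the same weakness. That limits the importance of the point but does not remove it.

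**Conclusion.** The point holds as an omission. The trial is open, the researchers are to compare a visually read sign across two scans, both within-arm and between-arm tests are planned, and masked reading is not provided for. Expectation could bias both comparisons. That the reader knows the arm and the scan order is a fair inference, not a written fact.

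Under the assumed rates, the chance of a false between-arm difference ranges from about nominal or below, when expectation moves readings by 5 to 10 percentage points, to 27.3–55.5% at 19 per arm (16.7–39.6% at 15) when it moves them by 20 to 30 points. The bias is therefore material only if readings shift substantially, and the documents cannot say whether they would. The primary endpoint, the sample size and α are untouched. This is a worthwhile low-cost improvement, not a flaw that threatens the main conclusion.

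**What to change.** In section 10.2, state that once both scans of all patients are collected, the head MRI/SWI series are stripped of identity, arm and date. They are then scored in random order, masked to arm and scan sequence, by whoever on the study team would otherwise read them, preferably someone not treating the patients. Change is computed only after the scores are locked.

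The cost is relabelling and shuffling at most 38 × 2 = 76 stored scans. No visit or scan is added, and no reader beyond the one the comparison already needs. There are three downsides:

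- Endpoint readings wait until all scans are in.
- Single-scan scoring may be less sensitive to small within-patient change; pairs shown with their order hidden are an alternative.
- Masking may be incomplete if the reader has already seen a scan clinically.

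The timing of the second scan also needs to be reconciled before the text is fixed. The visit schedule and section 8.3 place it at V4, 12 weeks (day 84). Section 10.2 places it on Day 10 of the third cycle, which under the section 7.2 pattern of 10 daily blocks and 20-day gaps falls near day 2 × (10 + 20) + 10 = 70, about week 10.
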